5.4 Study Time Intervals

Monthly Interval for Efficacy Endpoints

Monthly efficacy measurements will be calculated based on the 2-week IP dosing schedule defined below using eDiary data collected from the beginning of the baseline phase (week -4 visit) up to the end of the safety follow-up phase (week 28 end of eDiary use). Any eDiary data occurring after EOS date or after the end date of the last monthly interval defined below, whichever comes earlier, will not be included in the analysis.

Table 5-1. Monthly Interval for Efficacy Endpoints Derived From Daily eDiary Data

Study Phase	Assessment Time Point	Monthly Interval	
		Start Date/Day	End Date/Day
Baseline Phase	Baseline	eDiary device assignment date (week -4 visit)	The day of or prior to Study Day 1
Double-blind Treatment Phase	Week 4	Study Day 1	
• Week 4 dose date – 1• Else MIN(Study Day 28, EOS) if Week 4 dose was not received
	Week 8	
• Week 4 dose date• Else Study Day 29 if Week 4 dose was not received	
• Week 8 dose date – 1• Else MIN(Study Day 56, EOS) if Week 8 dose was not received
	Week 12	
• Week 8 dose date• Else Study Day 57 if Week 8 dose was not received	
• MIN(Study Day 84, EOS)
Safety Follow-up Period	Week 16	
• Study Day 85	
• MIN(Study Day 112, EOS)
	Week 20	
• Study Day 113	
• MIN(Study Day 140, EOS)
	Week 24	
• Study Day 141	
• MIN(Study Day 168, EOS)
	Week 28	
• Study Day 169	
• MIN(Study Day 196, EOS)

Study Visit

Since the actual visit for a subject may not exactly coincide with their targeted visit date, the actual visit date is mapped to the study visit as following. The study day window will be utilized to define study visit for lab, vital signs, physical measurements and PROs collected during office visits including HIT-6, and MMIDAS. Any data occurring after the EOS date will not be included in the analysis with the exception of lab shift analyses and antibody data.

Table 5-2. Study Visit Windows for HIT-6, MMIDAS, C-SSRS, and CAPS Scale

Study Phase	Study Visit	Target Day	Study Day
Double-blind Treatment Period	Baseline	Please refer to Section 5.3 Baseline Assessment of the Study	
	Week 4	29	• 2 – 43
	Week 8	57	• 44 – 71
	Week 12	85	• 72 – 99
Safety Follow-up Period	Week 16	113	• 100 – 127
	Week 20	141	• 128 – 155
	Week 24	169	• 156 – 183
	Week 28	197	• 184 – 211

Table 5-3. Study Visit Windows for Lab (Except HbA1C and Urinalysis)

Study Phase	Study Visit	Target Day	Study Day
Double-blind Treatment Period	Baseline	Please refer to Section 5.3 Baseline Assessment of the Study	
	Week 4	29	• 2 – 36
	Week 6	43	• 37 – 64
	Week 12	85	• 65 – 99
Safety Follow-up period	Week 20	141	• 100 – 169
	Week 28	197	• 170 – 211

Table 5-4. Study Visit Windows for HbA1C

Study Phase	Study Visit	Target Day	Study Day
Double-blind Treatment Period	Baseline	Please refer to Section 5.3 Baseline Assessment of the Study	
	Week 6	43	• 2 – 64
	Week 12	85	• 65 – 99
	Safety Follow-up period	141	• 100 – 169
		197	• 170 – 211

Table 5-5. Study Visits for Vital Signs

Study Phase	Study Visit	Target Day	Study Day
Double-blind Treatment Period	Baseline	Please refer to Section 5.3 Baseline Assessment of the Study	
	Day 1	1	• 1
	Week 2	15	• 2 – 22
	Week 4	29	• 23 – 36
	Week 6	43	• 37 – 50
	Week 8	57	• 51 – 64
	Week 10	71	• 65 – 78
Safety Follow-up period	Week 12	85	• 79 – 99
	Week 16	113	• 100 – 127
	Week 20	141	• 128 – 155
	Week 24	169	• 156 – 183
	Week 28	197	• 184 – 211

Table 5-6. Study Visits for Physical Examination

Study Phase	Study Visit	Target Day	Study Day
Double-blind Treatment Period	Baseline	Please refer to Section 5.3 Baseline Assessment of the Study	
	Week 12	85	• 1 – 99
Safety Follow-up period	Week 28	197	• 100 – 211

Table 5-7. Study Visits for PK

Study Phase	Study Visit	Target Day	Study Day
Double-blind Treatment Period	Baseline	Please refer to Section 5.3 Baseline Assessment of the Study	
	Week 1	8	• 2 – 15
	Week 4	29	• 16 – 43
	Week 8	57	• 44 – 60
	Week 9	64	• 61 – 67
	Week 10	71	• 68 – 78
	Week 12	85	• 79 – 99
Safety Follow-up period	Week 16	113	• 100 – 141
	Week 24	169	• 142 – 183
	Week 28	197	• 184 – 211

Table 5-8. Study Visits for Antibody

Study Phase	Study Visit	Target Day	Study Day
Double-blind Treatment Period	Baseline	Please refer to Section 5.3 Baseline Assessment of the Study	
	Week 8	57	• 2 – 71
	Week 12	85	• 72 – 99
Safety Follow-up period	Week 16	113	• 100 – 141
	Week 24	169	• 142 – 183
	Week 28	197	• 184 – 211

Note:

If more than one visit (including the unscheduled visits, ie, CPEVENT = 'UNSCHED') falls within the same defined window with non-missing measurements, **the closest visit to the target day will be considered for analysis**. If two assessment dates are equidistant from the target date, the latter visit will be considered for analysis. The baseline assessment is defined as the last non-missing measurement for the endpoint of interest taken before the first dose of IP. In cases where baseline measurements are taken on the same day as the first dose of IP **and the measurement time is not collected**, it will be assumed that these measurements are taken prior to IP being administered

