## 2.2 Schedule of Activities

**Table 2-1. Schedule of Activities**

Procedure	Screening Period (Up to 7 weeks)			Double-Blind Treatment Period a (12 weeks) (± 2 days)									Safety Follow-up Period (16 weeks) (± 5 days)			
	Screening up to 3 weeks	Baseline Period b		Day 1 (Post- rand) c	Wk 1	Wk 2	Wk 4	Wk 6	Wk 8	Wk 9	Wk 10	Wk 12/ET d	Wk 16	Wk 20	Wk 24	Wk 28/ET/ EOS d
		-4 Weeks	Pre- rand (Day 1)													
GENERAL AND SAFETY ASSESSMENTS																
Informed consent	X															
Physical examination	X												X			X
Height and Weight e	X		X										X			X
Demographics f	X															
Vital signs g	X	X	X h	X i		X	X	X	X		X	X	X	X	X	X
Medical and Medication history j	X		X													
12-lead ECG	X			X						X			X		X	X
Adverse events k	X	X	X	X	X	X	X	X	X	X	X	X	X	X	X	X
Concomitant medications	X			X	X	X	X	X	X	X	X	X	X	X	X	X
Product Complaints Recording				X		X	X	X	X		X					
LABORATORY ASSESSMENTS																
Serum pregnancy test l	X															
Urine Pregnancy test l			X					X		X			X			X

Page 1 of 3

Footnotes defined on last page of table

Table 2-1. Schedule of Activities

Procedure	Screening Period (Up to 7 weeks)			Double-Blind Treatment Period a (12 weeks) (± 2 days)									Safety Follow-up Period (16 weeks) (± 5 days)			
	Screening up to 3 weeks	Baseline Period b		Day 1 (Post- rand) c	Wk 1	Wk 2	Wk 4	Wk 6	Wk 8	Wk 9	Wk 10	Wk 12/ET d	Wk 16	Wk 20	Wk 24	Wk 28/ET/ EOS d
		-4 Weeks	Pre- rand (Day 1)													
Hepatitis B and Hepatitis C storage sample				X m												
Serum plasma glucose n	X															
HbA1c	X								X o				X o		X o	X o
Hematology, chemistry	X			X			X	X o				X o		X		X
Urinalysis	X											X				
Urine drug screen p	X															
RANDOMIZATION/INVESTIGATIONAL PRODUCT DOSING																
Call to IVR/IWR system q	X			X			X	X	X	X		X				X
Entry into the Baseline period		X														
Randomization			X													
Investigational Product				X r		X	X	X	X		X					
PK ASSESSMENTS																
PK Sampling (serum) s				X	X		X		X	X	X	X	X	X	X	X
BIOMARKER ASSESSMENTS																

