5.3 Study Points of Reference

Baseline Period

The 4-week baseline period starts when the subject has met all Part 1 eligibility criteria (refer to Section 6.1 of the protocol) and is entered in the baseline period (refer to Section 6.6 of the protocol) and ends when the subject is considered a screen failure (discontinuation before randomization and/or subject does not meet all baseline eligibility criteria, refer to [Section 6.3](#)) or randomized.

The first day of the baseline period is the day that the subject records the first assessment in the eDiary and the last day of this period is the date the subject records the last assessment prior to the first dose of IP on Study Day 1.

The baseline assessment is defined as the last non-missing measurement for the endpoint of interest taken before the first dose of IP. In cases where baseline measurements are taken on the same day as the first dose of IP, it will be assumed that these measurements are taken prior to IP being administered. For subjects who are randomized but not dosed after the randomization, the baseline of the study is defined as the last non-missing measurement prior to or on the date of randomization. Above definition applies to safety measurements and PROs collected at office **visits** (HIT-6, CAPS and MMIDAS).

For measurements with multiple individual items such as C-SSRS and ECG, all individual items from the same set of measurement will be used for analysis. If some items from the same set are missing, then the latest complete set of measurement prior to the first dose of IP will be used as baseline. A similar rule holds for post-baseline measurements.

Baseline assessment of data collected from eDiary will be summarized as monthly measurements using data collected during baseline period.

Study Day 1

Study Day 1 is defined as the first IP dose date. For subjects who are randomized but not dosed after randomization, the Study Day 1 is defined as the date of randomization.

Study Day

Study Day is defined as the number of days from Study Day 1.

Before Study Day 1:

Study Day = (date of interest – date of Study Day 1)

On or after Study Day 1:

Study Day = (date of interest – date of Study Day 1) + 1

Therefore the day prior to Study Day 1 is -1.

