9.6.7 Physical Measurements

The analyses of weight will include summary statistics over time by treatment group. The number and percentage of subjects with at least one post-treatment weight measurement meeting the following criteria will be reported:

Decrease of 7% from baseline or increase of 7% from baseline

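### SAP Table 5-6 opens the Week 12 window on Study Day 1, so a subject with no weight on Days 2–99 has the pre-dose Day 1 weight reported as Week 12

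*SAP*

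**What the plan says.** SAP 5.4 sets the scope of the windows: "The study day window will be utilized to define study visit for lab, vital signs, physical measurements and PROs collected during office visits". The tables that follow cover HIT-6 and similar scales (5-2), laboratory tests (5-3), HbA1c (5-4), vital signs (5-5), physical examination (5-6), PK (5-7) and antibodies (5-8). In "Table 5-6. Study Visits for Physical Examination", the Baseline row points to Section 5.3, Week 12 (target Day 85) covers Study Days 1–99, and Week 28 (target Day 197) covers Days 100–211.

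Where several records fall in one window, the note after Table 5-8 says that "the closest visit to the target day will be considered for analysis", with the later record used if two are equidistant.

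SAP 5.3 fixes the reference points: "Study Day 1 is defined as the first IP dose date" and "The baseline assessment is defined as the last non-missing measurement for the endpoint of interest taken before the first dose of IP". For a value taken on the dosing day, "it will be assumed that these measurements are taken prior to IP being administered"; the note in 5.4 limits this to cases where no measurement time was collected.

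The protocol's Schedule of Activities (Table 2-1) marks weight at screening, at the pre-randomization Day 1 visit, and at two later visits, which Table 5-6 takes as Weeks 12 and 28. SAP 9.6.7 plans summary statistics of weight over time, plus a count of subjects with "at least one post-treatment weight measurement meeting the following criteria", namely a 7% decrease or increase from baseline. SAP 8.3 leaves missing safety endpoints unimputed, apart from adverse event dates.

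**The concern.** Day 1 is the day of the baseline weight, yet Table 5-6 puts it inside the Week 12 window. Nothing in the SAP says that a record already used as baseline is barred from a later window. A subject who never has a weight taken during treatment should have a missing Week 12 value. Under the rules as written, that subject has one record counted twice, once as baseline and once as Week 12.

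The protocol's benefit/risk section lists body weight among the measures used to assess energy metabolism, so the by-visit weight table is one that a safety reader will consult. Its Week 12 column would contain pre-treatment weights with no sign that they are such, and its count of subjects with a Week 12 weight would be too high.

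**Working it through.** No sample-size, power or alpha figure is involved. The check compares the window limits and then applies the selection rule.

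**1. First post-baseline window in each table of SAP 5.4**

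| Table | First row after Baseline | Days |
|---|---|---|
| 5-2 | Week 4 | 2–43 |
| 5-3 | Week 4 | 2–36 |
| 5-4 | Week 6 | 2–64 |
| 5-5 | Day 1, then Week 2 | 1, then 2–22 |
| 5-6 | Week 12 | 1–99 |
| 5-7 | Week 1 | 2–15 |
| 5-8 | Week 8 | 2–71 |

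Table 5-6 is the only one in which Day 1 falls inside a later scheduled week.

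**2. Which measurement is exposed.** The examination named in the title of Table 5-6 is not scheduled on Day 1, so the start day makes no difference to it. Weight is scheduled that day, before randomization, and Table 2-1 footnote c puts randomization before the first dose. The Day 1 weight is therefore pre-dose by schedule, whether or not a clock time was recorded.

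**3. When the rule picks Day 1.** Distance from target = |day − 85|.

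- Day 1: |1 − 85| = 84
- Day 2: |2 − 85| = 83, the largest distance on Days 2–99
- Day 99: |99 − 85| = 14

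Day 1 loses to any weight on Days 2–99 and is selected only when there is none.

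**4. Applying the rule to example subjects**

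| Weights available | Week 12 value, window 1–99 | Week 12 value, window 2–99 |
|---|---|---|
| Screening, Day 1 | Day 1 | missing |
| Screening, Day 1, Day 197 | Day 1 | missing |
| Screening, Day 1, Day 2 | Day 2 | Day 2 |
| Screening, Day 1, Day 85 | Day 85 | Day 85 |
| Screening, Day 1, Day 99 | Day 99 | Day 99 |
| Screening only | missing | missing |

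The second row shows that a Week 28 weight does not prevent the problem, because it lies in the window for Days 100–211. The next three rows show that a 2–99 window changes no genuine post-baseline value.

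**5. Number affected.** The documents give no figure. As an assumption only: 335 × 0.02 = 6.7, 335 × 0.05 = 16.75 and 335 × 0.10 = 33.5, or about 7, 17 and 34 subjects across the three arms.

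**The case against.** **The table may not govern weight.** Its title refers to the physical examination, so its use for weight is inferred. The inference is sound: SAP 5.4 says physical measurements are windowed, no other table fits them, SAP 9.6 plans no analysis of examination findings, and SAP 9.6.7 is about weight. The title still leaves room for doubt, which the SAP should remove.

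**A sensible programmer would keep baseline out of the Week 12 row.** Table 5-6 has its own Baseline row, and SAP 5.3 and 5.6 speak of baseline and post-baseline values separately. That may well be the intention, but no sentence states it, and the other tables achieve it by starting on Day 2. The Day 1 row of Table 5-5 could, read literally, also take in a pre-dose vital sign, but it would still be labelled Day 1 and not a later week.

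**The affected group is small.** Subjects who stop product or leave during treatment are to complete the Week 12/ET visit (protocol Table 2-1 footnote d and 9.1.5), and those who stop product are asked to continue all procedures (7.4.3.1). This stands. The exposure is limited to subjects who have no weight at that visit or at any other time on Days 2–99.

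**Stronger readings that a reader might infer.** One is that the mean Week 12 weight change shrinks in proportion to the share affected, for example by 5% to 10%. The documents do not support this: SAP 9.6.7 and protocol 10.4.3.3.5 plan summary statistics over time for weight. A change-from-baseline summary is stated for vital signs and laboratory values, and weight is not among the vital signs. The other is that the 7% count is diluted. That count is restricted to post-treatment weights, a pre-dose weight is not one, and a change of zero cannot reach 7% in either direction. Whether these subjects would enter its denominator is speculation, since the SAP does not define that denominator through Table 5-6.

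**Conclusion.** The window is wrong as written, with a minor consequence. For a subject with a Day 1 weight and none on Days 2–99, the SAP's rules report the baseline weight as the Week 12 weight, which conflicts with its own rule against imputing missing safety endpoints. What is exposed is one descriptive safety summary, with no statistical testing attached to it.

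This rests on two assumptions: that Table 5-6 is the table meant for weight, and that baseline records are not silently excluded in programming. The judgment that few subjects are affected assumes that the Week 12/ET visit includes a weight, as the Week 12 target in Table 5-6 implies, and that it is mostly attended. The true number is unknown before data are collected.

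**What to change.** In SAP Table 5-6, change the Week 12 window from 1–99 to 2–99. Alternatively, add a sentence to the note in SAP 5.4 saying that a record used as baseline is not eligible for any post-baseline window. In either case, state in the title or a footnote that Table 5-6 applies to weight.

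The cost is one digit and a short clarification in the SAP. No data collection, protocol text or efficacy analysis is touched.

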- c. Randomization (day 1 pre-randomization) into the double-blind treatment phase using the IVR/IWR system must occur only after completion of all baseline period procedures and before the first dose of double-blind investigational product (randomization and administration of the first dose of investigational product should occur on day 1).
- d. A subject who discontinues investigational product or the study during the double-blind treatment period will complete the week 12/ET visit. Subjects who discontinue after the double-blind treatment period (week 12) and before week 28 will complete the week 28/EOS/ET visit.
- e. Height and weight will be measured without shoes. Height will be collected at the screening visit only.
- f. Demographics will include sex, age, race and ethnicity.
- g. **Vital signs will be assessed prior to investigational product administration, and** will include systolic/diastolic blood pressure, heart rate, respiratory rate, and body temperature. Subject must be in a supine position in a rested and calm state for at least 5 minutes before blood pressure assessments are conducted. If the subject is unable to be in the supine position, the subject should be in most recumbent position as possible. The position selected for a subject should be the same that is used throughout the study.
- h. **Vital signs will be assessed prior to subject registration using the IVR/IWR system.**
- i. **Vital signs will be assessed approximately 30 to 60 minutes after investigational product administration.**
- j. Medical history will include targeted cardiologic, neurologic, psychiatric, cardiovascular, and history of diabetes, including gestational diabetes and/or impaired glucose tolerance testing. A history of participation in prior Amgen studies will be included. Medication history to include prior migraine prophylactic treatment history within the 90 days before screening will be collected.
- k. Serious adverse events are to be collected after signing of the informed consent through EOS (18 weeks after the last dose investigational product). Adverse events are to be collected after the first dose of investigational product through EOS (18 weeks after the last dose of investigational product). Disease related events are to be collected after the first dose of investigational product through 18 weeks after the last dose of investigational product (EOS).

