5.1.2 Safety Endpoints

Treatment-emergent Adverse Event (TEAE)

An adverse Event (AE) recorded on the Events eCRF page that occurs on or after the date of the first dose of investigational product (IP), as determined by the flag indicating the event did not start before first dose of IP on the Events eCRF, and up to and including **126 days** after the end of IP (ie. **18 weeks** after the last dose of IP).

Serious TEAE

A serious treatment-emergent adverse event is an SAE considered to be treatment-emergent.

Disease-Related Event (DRE)

Disease-related Events (DREs) are events determined by the flag on the Event CRF.

Columbia-Suicide Severity Rating Scale (C-SSRS)

The C-SSRS is a clinician rating of suicidal behavior and ideation. Two versions depending on the type of visits will be used in this study: Screening and Since Last Visit. The C-SSRS consists of a maximum of 20 items, which defines 5 subtypes of suicidal ideation and behavior in addition to self-injurious behavior with no suicidal intent. The C-SSRS will be administered by the principal investigator or qualified designee to evaluate suicidal behavior and suicidal ideation. For the baseline assessment, for measurements with multiple individual items, all individual items from the same set of measurement will be used for analysis.

For C-SSRS, the last complete assessment prior to first IP administration will be used as the baseline. If subject completes C-SSRS form on Day 1 then all individual items from Day 1 visit will be used as baseline. If subject does not complete C-SSRS form on Day 1 then all individual items from Week -4 visit will be used as baseline. Please refer to [Appendix E](#) for more information.

Beck Depression Inventory (BDI)-II

The BDI-II is a 21-item questionnaire that assesses severity of depression. Each item is scored from 0 to 3. The total score is categorized into 4 severity grades: Minimal depression (0-13), mild depression (14-19), moderate depression (20-28) and severe depression (29-63). Please refer to Appendix E for more information.

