9.6.6 Columbia Suicide Severity Rating Score (C-SSRS)

No statistical testing will be performed on C-SSRS. The number and percentage of subjects in each of the 5 categories describing suicidal behavior and ideation will be summarized by treatment group.

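### Followed as written, the SAP's closest-visit rule can leave a positive early-termination or unscheduled C-SSRS form out of the by-arm suicidality summary

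*SAP*

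**What the plan says.** **Windows.** The title of SAP Table 5-2 is "Study Visit Windows for HIT-6, MMIDAS, C-SSRS, and CAPS Scale". The windows are Days 2-43 (target 29), 44-71 (target 57), 72-99 (target 85), and then 28-day windows up to Days 184-211 (target 197).

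**Selection within a window.** The note after Table 5-8 reads: "If more than one visit (including the unscheduled visits, ie, CPEVENT = 'UNSCHED') falls within the same defined window with non-missing measurements", then "the closest visit to the target day will be considered for analysis". For ties: "If two assessment dates are equidistant from the target date, the latter visit will be considered for analysis". Selection depends on the date alone.

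**Instrument.** SAP 5.1.2: "Two versions depending on the type of visits will be used in this study: Screening and Since Last Visit".

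**Summary.** SAP 9.6.6: "The number and percentage of subjects in each of the 5 categories describing suicidal behavior and ideation will be summarized by treatment group". It does not say whether this is by visit, at any time or worst post-baseline, and it plans no listing. SAP 9.1 says generally that summaries by treatment group are tabulated at each visit.

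**ET visits.** Protocol Table 2-1, footnote d: "A subject who discontinues investigational product or the study during the double-blind treatment period will complete the week 12/ET visit". The C-SSRS is scheduled at that visit and at the Week 28/ET/EOS visit.

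**The concern.** Keeping the form nearest the target day suits a repeated measure of current state such as the HIT-6, where one value stands in reasonably for another. A Since Last Visit form works differently. It reports what happened in one interval, and the next form starts where it stopped. Discarding a form therefore discards observation time, and any ideation or behaviour recorded in that time.

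Protocol 3.3 names suicidal risk monitoring by C-SSRS, with physical and neurological examination, as the assessment of central nervous system impact. Subjects with ideation of severity 4 or 5 or any suicidal behaviour at screening or baseline are excluded (criteria 219 and 237), so few positive forms are likely and each one counts. Splitting 335 subjects 4:3:3 gives about 134 on placebo and 100.5 per active arm. One omitted positive subject moves an arm's incidence by 1/100.5 = 1.0 percentage point (active) or 1/134 = 0.75 (placebo).

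**Working it through.** The plan states no figure to reproduce. The check applies the SAP 5.4 rule (smallest |form day − target day|, later form on a tie) to the Table 5-2 windows.

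**1. Single cases**
- Week 4 form on Day 29, negative; ET form on Day 40, positive. Both fall in Days 2-43. Distances are |29 − 29| = 0 and |40 − 29| = 11. Day 29 is kept and the positive form is dropped.
- Unscheduled form on Day 24, positive; Week 4 form on Day 29, negative for the time since Day 24. Distances are 5 and 0. The positive form is dropped.

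**2. Any extra form, scheduled form on target.** An extra form on any other day of the same window loses. The windows cover Days 2-211, or 210 days, and contain 7 target days, so the extra form is dropped on 210 − 7 = 203 days.

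**3. Scheduled form off target.** One of the two forms is still always dropped.
- Week 4 visit on Day 27 (the ±2-day limit): the extra form is dropped on 37 of the 41 other window days. On the other 4 (Days 28-31) the scheduled form is dropped instead.
- Week 16 visit on Day 108 (the ±5-day limit): the extra form is dropped on 17 of 27 days and the scheduled form on 10.

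**4. Share of study-withdrawal ET forms dropped.** Assumptions: the subject leaves the study at the ET visit, ET dates are spread evenly over days, and earlier scheduled visits fell on target. An ET form is then dropped only if a scheduled form already sits in the same window, that is, in the 14 days after a target.
- Days 2-28: no Week 4 form exists, so the ET form stands alone and is kept.
- Days 2-84 (83 days): dropped on Days 30-43 and 58-71, so 28/83 = 34%.
- Days 2-197 (196 days): dropped in the 14 days after each of the targets 29, 57, 85, 113, 141 and 169, so 6 × 14 = 84 and 84/196 = 43%.

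Subjects who stop product but stay in the study are a separate case. Protocol 7.4.3.1 asks them to keep attending, so a later scheduled form can also displace their ET form, as in step 2.

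**5. Does any other text restore the dropped form?** For other measures the SAP writes an explicit rule:
- vital signs and weight: at least one post-treatment value meeting a criterion (9.6.4, 9.6.7);
- HIT-6 and MMIDAS shifts: the most extreme post-baseline value (9.5.4);
- antibodies: a list of subjects positive at any time (9.6.9).

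Section 9.6.6 has no counterpart for the C-SSRS.

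**The case against.** **The link to 9.6.6 is an inference.** That section describes a count of subjects by arm and names no visit, whereas 9.6.4 says so explicitly when it means each time point. A programmer could read 9.6.6 as counting any post-baseline form. This stands as a reason to call the loss possible. It does not remove the problem, because the only written selection rule and the general by-visit instruction in 9.1 both point towards discarding.

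**The windows may not govern the C-SSRS.** The sentence introducing them in 5.4 lists laboratory, vital-sign, physical and office-visit PRO data and omits the C-SSRS, which is a clinician rating. Only the Table 5-2 title includes it. This also stands, and shows that the SAP needs to settle the question.

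**Appendix E is redacted.** SAP 5.1.2 refers there for more on the C-SSRS, so a derivation rule may exist that cannot be seen. The recall wording is likewise not visible; interval recall is inferred from the version's name.

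**There is a backstop.** Events meeting the AE or SAE definition are tabulated under SAP 9.6.2 regardless of visit windows, and the Data Review Team reviews safety. This is true, but it does not put the event back into the C-SSRS summary. Protocol 9.2.3.5.1 asks for management by standard of care and does not itself say that a positive form is recorded as an AE.

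**Stronger readings that the documents do not support.**
- A reader might infer that half of ET forms are lost, because the windows run 14 days past each target in a 28-day cycle (14/28). That ignores the longer first window, where ET forms on Days 2-28 stand alone.
- A reader might infer that the dropped forms come from the subjects most likely to be positive, or that the loss differs by arm. The documents give no rate of positive forms and no discontinuation figures by arm.
- Unscheduled C-SSRS use is also hypothetical: the protocol ties administration to Table 2-1.

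**Conclusion.** The point holds as a defect in the written rule: applied literally, it can give a wrong count in the by-arm C-SSRS summary. Whether any positive form would be lost depends on how 9.6.6 is programmed, on what Appendix E contains, and on whether a positive extra form shares a window with a form nearer the target.

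The illustrative shares of 34% over Days 2-84 and 43% through Day 197 refer to all study-withdrawal ET forms, not to positive ones. They rest on evenly spread ET dates and on-target scheduled visits, neither of which the documents establish. The C-SSRS summary is descriptive and untested, and the efficacy analyses are unaffected. The change should be made because it is cheap and the summary exists to show rare events.

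**What to change.** - **SAP 9.6.6:** summarise, by arm, each subject's worst post-baseline C-SSRS category over all post-dose assessments, including ET and unscheduled visits. A listing of positive forms would help.
- **SAP 5.4:** exempt the C-SSRS from the closest-visit rule. If a by-visit table is kept, use the worst value in the window. Make the introductory sentence and the Table 5-2 title agree on whether the C-SSRS is windowed.

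**Cost:** SAP wording and one extra derivation, using data already collected. Reported incidence may be slightly higher than under the present rule.
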